### 9.5.3 Safety Analyses

All analyses based on safety data (AEs, laboratory data, ECGs, vital signs, and physical exam data) will be based on the Safety population.

AE terms recorded on the eCRFs will be mapped to preferred terms using the Medical Dictionary for Regulatory Activities (MedDRA®) version 17.0 or later. AEs included in summary tables will be restricted to treatment-emergent AEs (TEAEs). A TEAE is defined as an AE that occurs (or worsens) after study drug is received. TEAEs will be summarized for each treatment group by the

number and percentage of patients who experienced the event, according to the system organ class and preferred term. Additional summaries will also be provided by severity and relationship to study drug. Listings of deaths, SAEs and AEs leading to early termination of study drug or premature withdrawal from study will also be provided.

Descriptive statistics will be provided for laboratory results by scheduled time of evaluation and by treatment group, as well as for change from baseline. Laboratory variables will be evaluated using mean change in value from baseline to scheduled time points. The baseline value of a variable is defined as the last value obtained on or before the date and time of the first study drug dose. Individual laboratory test results that are outside the normal range for that test will be flagged as high (H) or low (L), as appropriate, in the listings.

ECGs, vital sign measurements and weight will be summarized by change from baseline to scheduled time points using descriptive statistics.

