4.8.1 Adverse Events

An AE is defined as any untoward medical occurrence in a subject who is administered a medicinal product and that does not necessarily have a causal relationship to the treatment. All AEs will be included in the data listings. Verbatim terms on case report forms will be mapped to preferred terms and system organ classes (SOC) using the Medical Dictionary for Regulatory Activities (MedDRA) (version 19.1).

A Treatment Emergent Adverse Event (TEAE) is defined as an adverse event that occurs or worsens on or after the first dose of study drug. TEAE summary will be displayed by cohort and treatment. Unless otherwise specified, summaries that are displayed by SOC and preferred terms will be ordered alphabetically by SOC, and within each SOC, preferred terms will also be ordered alphabetically. Summaries of the following types will be presented:

- Subject incidence of TEAEs by MedDRA SOC and preferred term.
- Subject incidence of TEAEs by MedDRA SOC, preferred term, and severity. Severity will be recorded as deemed by investigator. At each level of subject summarization, a subject is classified according to the highest severity if the subject reported one or more events.
- Subject incidence of study drug related TEAEs by MedDRA SOC and preferred term.
- Subject incidence of TEAEs by descending incidence of preferred terms.
- Subject incidence of serious TEAEs by MedDRA SOC and preferred term, if applicable.
- Subject incidence of TEAE leading to early termination by MedDRA SOC and preferred term, if applicable.

For each subject and for each adverse event, the duration of the event will be calculated as:

$$\text{Duration of AE} = \text{AE stop date} - \text{AE start date} + 1$$

The duration of AEs will be displayed in the data listing.

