5 CHANGES TO PROTOCOL-SPECIFIED ANALYSES

No changes to protocol-specified analyses are planned.

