6 LIST OF TABLES AND FIGURES

List of Tables

ICH Heading	Table Number	Table Description
14.1	14.1.1	DEMOGRAPHIC Summary of Patient Disposition (All Patients)
	14.1.2	Summary of Demographic and Baseline Characteristics (mITT Analysis set)
	14.1.3	Summary of Medical History (mITT Analysis set)
	14.1.4	Summary of Prior Medications (mITT Analysis set)
	14.1.5	Summary of Concomitant Medications (mITT Analysis set)
14.2		EFFICACY
14.2.1	14.2.1.1	Primary Efficacy Summary of Change of Total Mayo Score from Baseline to Week 8 (mITT Analysis set)
	14.2.1.2	Summary of Change of Total Mayo Score from Baseline to Week 8 (PP Analysis set)
14.2.2		Secondary Efficacy
	14.2.2.1.1	Summary of Change of Partial Mayo Score from Baseline to Week 8 (mITT Analysis set)
	14.2.2.1.2	Summary of Change of Partial Mayo Score from Baseline to Week 8 (PP Analysis set)

- 14.2.2.2.1 Summary of Change of Histologic Assessment of Endoscopic Biopsy from Baseline to Week 8 (mITT Analysis set)
- 14.2.2.2.2 Summary of Change of Histologic Assessment of Endoscopic Biopsy from Baseline to Week 8 (PP Analysis set)
- 14.2.2.3.1 Summary of Change of Ulcerative Colitis Endoscopic Index of Severity (UCEIS) Score from Baseline to Week 8 (mITT Analysis set)
- 14.2.2.3.2 Summary of Change of Ulcerative Colitis Endoscopic Index of Severity (UCEIS) Score from Baseline to Week 8 (PP Analysis set)
- 14.2.2.4.1 Summary of Change of Short Inflammatory Bowel Disease Questionnaire (SIBDQ) from Baseline to Week 8 (mITT Analysis set)
- 14.2.2.4.2 Summary of Change of Short Inflammatory Bowel Disease Questionnaire (SIBDQ) from Baseline to Week 8 (PP Analysis set)
- 14.2.3 Exploratory Efficacy**
 - 14.2.3.1 Summary of Change of Concentration of Biomarkers from Baseline to Week 8 (mITT Analysis set)
 - 14.2.3.2 Summary of Change of Concentration of Biomarkers from Baseline to Week 8 (PP Analysis set)
- 14.3 SAFETY**
 - 14.3.1 Display of Adverse Events**
 - 14.3.1.1 Overall Summary of Treatment-Emergent Adverse Events up to Week 8 (Safety Analysis set)
 - 14.3.1.2 Summary of Treatment-Emergent Adverse Events up to Week 8 by System Organ Class and Preferred Term (Safety Analysis set)
 - 14.3.1.3 Summary of Treatment-Emergent Adverse Events up to Week 8 by System Organ Class, Preferred Term, and Severity (Safety Analysis set)
 - 14.3.1.4 Summary of Treatment-Emergent Adverse Events up to Week 8 by System Organ Class, Preferred Term, and Relationship to Study Drug (Safety Analysis set)

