 - 14.3.1.5 Summary of Treatment-Emergent Serious Adverse Events up to Week 8 by System Organ Class and Preferred Term (Safety Analysis set)
 - 14.3.1.6 Summary of Treatment-Emergent Adverse Events up to Week 8 Leading to Study Discontinuation by System Organ Class and Preferred Term (Safety Analysis set)
 - 14.3.2 Laboratory Testings**
 - 14.3.2.1 Summary of Values and Changes of Hematology Parameters by Visit (Safety Analysis set)
 - 14.3.2.2 Summary of Values and Changes of Chemistry Parameters by Visit (Safety Analysis set)
 - 14.3.3 Vital Signs, ECG Data, Physical Examination**
 - 14.3.3.1 Summary of Vital Sign Parameters by Visit (Safety Analysis set)
 - 14.3.3.2 Summary of Electrocardiogram Parameters by Visit (Safety Analysis set)
 - 14.3.3.3 Summary of Physical Examination by Visit (Safety Analysis set)
- 14.4 Pharmacokinetics**
 - 14.4.1 Plasma Concentration**
 - 14.4.1.1 Plasma BBT-401-1S Concentrations (ng/mL) Following the Administration of BBT-401-1S or Placebo (PK Analysis set)
 - 14.4.2 Tissue Concentration**
 - 14.4.2.1 Tissue BBT-401-1S Concentrations (ng/g) Following the Administration of BBT-401-1S or Placebo (PK Analysis set)

List of Data Listings

ICH Heading	Listing Number	Listing Description
16.2		PATIENT DATA LISTINGS
16.2.1		Discontinued Patients
	16.2.1.1	Patient Disposition
16.2.2		Protocol Deviations
	16.2.2.1	Inclusion/Exclusion Criteria Findings – Deviations
16.2.3		Patients Excluded from the Efficacy Summary
16.2.4		Demographics and Baseline Characteristics
	16.2.4.1	Demographics and Baseline Characteristics
	16.2.4.2	Medical History
	16.2.4.3	Prior and Concomitant Medications
16.2.5		Compliance and/or Drug Administration Data
	16.2.5.1.1	Study Drug Administration and Log
16.2.6		Individual Efficacy Response Data
	16.2.6.1	Total Mayo Score
	16.2.6.2	Partial Mayo Score
	16.2.6.3	Histologic Assessment of Endoscopic Biopsy
	16.2.6.4	Ulcerative Colitis Endoscopic Index of Severity
	16.2.6.5	Short Inflammatory Bowel Disease Questionnaire
	16.2.6.6	Biomarkers
16.2.7		Adverse Events Listings
	16.2.7.1	Adverse Events
	16.2.7.2	Serious Adverse Events
	16.2.7.3	Adverse Events Leading to Permanent Withdrawal of Study Treatment or Discontinuation from the Study
	16.2.7.4	Adverse Events Leading to Death
16.2.8		Individual Lab Measures
	16.2.8.1	Hematology
	16.2.8.2	Chemistry
	16.2.8.3	Vital Signs
	16.2.8.4	Electrocardiogram
	16.2.8.5	Physical Examination
16.2.9		Pharmacokinetics
	16.2.9.1	Individual Plasma Concentration Data

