	16.2.9.2	Individual Tissue Concentration Data
16.2.10		Other Miscellaneous Data
	16.2.10.1	Randomization
	16.2.10.2	IP
	16.2.10.3	Investigator Signature

TABLES, FIGURES, AND LISTINGS SHELLS

Study Title: A Randomized, Double-blind, Placebo-controlled, Phase 2a Study to Evaluate the Efficacy and Safety of BBT-401-1S in Patients with Active Ulcerative Colitis

Sponsor: Bridge Biotherapeutics, Inc.
[name]
[name]
[name]

US Representative: KCRN Research, LLC.
[name]
[name]

Protocol Number: BBT401-UC-US02
Project Code: BBT401P2A

Version: 2.1 Final
Date: 22 Jul 2020

Tables and Listings to Be Generated

ICH Heading	Table Number	Table Description
14.1		DEMOGRAPHIC
	14.1.1	Summary of Patient Disposition (All Patients)
	14.1.2	Summary of Demographic and Baseline Characteristics (mITT Analysis set)
	14.1.3	Summary of Medical History (mITT Analysis set)
	14.1.4	Summary of Prior Medications (mITT Analysis set)
	14.1.5	Summary of Concomitant Medications (mITT Analysis set)
14.2		EFFICACY
14.2.1		Primary Efficacy
	14.2.1.1	Summary of Change of Total Mayo Score from Baseline to Week 8 (mITT Analysis set)
	14.2.1.2	Summary of Change of Total Mayo Score from Baseline to Week 8 (PP Analysis set)
14.2.2		Secondary Efficacy
	14.2.2.1.1	Summary of Change of Partial Mayo Score from Baseline to Week 8 (mITT Analysis set)
	14.2.2.1.2	Summary of Change of Partial Mayo Score from Baseline to Week 8 (PP Analysis set)
	14.2.2.2.1	Summary of Change of Histologic Assessment of Endoscopic Biopsy from Baseline to Week 8 (mITT Analysis set)
	14.2.2.2.2	Summary of Change of Histologic Assessment of Endoscopic Biopsy from Baseline to Week 8 (PP Analysis set)
	14.2.2.3.1	Summary of Change of Ulcerative Colitis Endoscopic Index of Severity (UCEIS) Score from Baseline to Week 8 (mITT Analysis set)
	14.2.2.3.2	Summary of Change of Ulcerative Colitis Endoscopic Index of Severity (UCEIS) Score from Baseline to Week 8 (PP Analysis set)
	14.2.2.4.1	Summary of Change of Short Inflammatory Bowel Disease Questionnaire (SIBDQ) from Baseline to Week 8 (mITT Analysis set)
	14.2.2.4.2	Summary of Change of Short Inflammatory Bowel Disease Questionnaire (SIBDQ) from Baseline to Week 8 (PP Analysis set)
14.2.3		Exploratory Efficacy
	14.2.3.1	Summary of Change of Concentration of Biomarkers from Baseline to Week 8 (mITT Analysis set)

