LS Mean (SE)	XX.X (XX.XX)	XX.X (XX.XX)
P-Value, Active vs Placebo	0.XXX	
LS Mean Difference (SE)	XX.X (XX.XX)	
95% CI for Differences	(XX.X, XX.X)	
Biomarker #2		
...		

Note: Least Squares means, p-values were from MMRM model with treatment and baseline score as fixed effects, and center as random effect. Restricted Maximum Likelihood (REML) with an unstructured variance-covariance matrix is used for estimation in the MMRM analysis.

Programming Note: Start a new page for each biomarker. This should include C-reactive protein [CRP], fecal calprotectin, and fecal lactoferrin.

Table 14.3.1.1
Overall Summary of Treatment-Emergent Adverse Events up to Week 8
Safety Analysis Set

	Placebo (N=XX)	BBT-401-1S (N=XX)	Overall (N=XX)
Number of Patients with at Least 1 TEAE up to Week 8	XX (XX.X)	XX (XX.X)	XX (XX.X)
Number of Patients with at Least 1 Serious TEAE up to Week 8	XX (XX.X)	XX (XX.X)	XX (XX.X)
Number of Patients with at Least 1 TEAE up to Week 8 Leading to Study Discontinuation	XX (XX.X)	XX (XX.X)	XX (XX.X)
Number of Patients with TEAEs by Worst Severity			
Mild	XX (XX.X)	XX (XX.X)	XX (XX.X)
Moderate	XX (XX.X)	XX (XX.X)	XX (XX.X)
Severe	XX (XX.X)	XX (XX.X)	XX (XX.X)
Number of Patients with TEAEs by Worst Relationship			
Not Related	XX (XX.X)	XX (XX.X)	XX (XX.X)
Possibly Related	XX (XX.X)	XX (XX.X)	XX (XX.X)
Probably Related	XX (XX.X)	XX (XX.X)	XX (XX.X)
Related	XX (XX.X)	XX (XX.X)	XX (XX.X)

Note 1: A Treatment Emergent Adverse Event (TEAE) is defined as an adverse event that occurs or worsens on or after the first dose of study drug.

Note 2: If a patient experienced more than 1 event in a category, then that patient is counted only once in that category.

Note 3: MedDRA Dictionary (Version 23.0) was used for coding adverse events.

Output ID: <Unique Output id i.e. t-enrol> Draft-DDMMYYYY HH:MM:SS DATE OF DATABASE EXTRACTION: DDMMYYYY
<Path/Program Name> Page 1 of X

Table 14.3.1.2
Summary of Treatment-Emergent Adverse Events up to Week 8 by System Organ Class and Preferred Term
Safety Analysis set

System Organ Class Preferred Term	Placebo (N=XX)	BBT-401-1S (N=XX)	Overall (N=XX)
Subjects with Any TEAEs up to Week 8	XX (XX.X)	XX (XX.X)	XX (XX.X)
System Organ Class 1	XX (XX.X)	XX (XX.X)	XX (XX.X)
Preferred Term 1	XX (XX.X)	XX (XX.X)	XX (XX.X)
Preferred Term 2	XX (XX.X)	XX (XX.X)	XX (XX.X)
...			
System Organ Class 2	XX (XX.X)	XX (XX.X)	XX (XX.X)
Preferred Term 1	XX (XX.X)	XX (XX.X)	XX (XX.X)
Preferred Term 2	XX (XX.X)	XX (XX.X)	XX (XX.X)
...			

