 - 14.3.1.5 Summary of Treatment-Emergent Serious Adverse Events up to Week 8 by System Organ Class and Preferred Term (Safety Analysis set)
 - 14.3.1.6 Summary of Treatment-Emergent Adverse Events up to Week 8 Leading to Study Discontinuation by System Organ Class and Preferred Term (Safety Analysis set)
 - 14.3.2 Laboratory Testings**
 - 14.3.2.1 Summary of Values and Changes of Hematology Parameters by Visit (Safety Analysis set)
 - 14.3.2.2 Summary of Values and Changes of Chemistry Parameters by Visit (Safety Analysis set)
 - 14.3.3 Vital Signs, ECG Data, Physical Examination**
 - 14.3.3.1 Summary of Vital Sign Parameters by Visit (Safety Analysis set)
 - 14.3.3.2 Summary of Electrocardiogram Parameters by Visit (Safety Analysis set)
 - 14.3.3.3 Summary of Physical Examination by Visit (Safety Analysis set)
- 14.4 Pharmacokinetics**
 - 14.4.1 Plasma Concentration**
 - 14.4.1.1 Plasma BBT-401-1S Concentrations (ng/mL) Following the Administration of BBT-401-1S or Placebo (PK Analysis set)
 - 14.4.2 Tissue Concentration**
 - 14.4.2.1 Tissue BBT-401-1S Concentrations (ng/g) Following the Administration of BBT-401-1S or Placebo (PK Analysis set)

List of Data Listings

ICH Heading	Listing Number	Listing Description
16.2		PATIENT DATA LISTINGS
16.2.1		Discontinued Patients
	16.2.1.1	Patient Disposition
16.2.2		Protocol Deviations
	16.2.2.1	Inclusion/Exclusion Criteria Findings – Deviations
16.2.3		Patients Excluded from the Efficacy Summary
16.2.4		Demographics and Baseline Characteristics
	16.2.4.1	Demographics and Baseline Characteristics
	16.2.4.2	Medical History
	16.2.4.3	Prior and Concomitant Medications
16.2.5		Compliance and/or Drug Administration Data
	16.2.5.1.1	Study Drug Administration and Log
16.2.6		Individual Efficacy Response Data
	16.2.6.1	Total Mayo Score
	16.2.6.2	Partial Mayo Score
	16.2.6.3	Histologic Assessment of Endoscopic Biopsy
	16.2.6.4	Ulcerative Colitis Endoscopic Index of Severity
	16.2.6.5	Short Inflammatory Bowel Disease Questionnaire
	16.2.6.6	Biomarkers
16.2.7		Adverse Events Listings
	16.2.7.1	Adverse Events
	16.2.7.2	Serious Adverse Events
	16.2.7.3	Adverse Events Leading to Permanent Withdrawal of Study Treatment or Discontinuation from the Study
	16.2.7.4	Adverse Events Leading to Death
16.2.8		Individual Lab Measures
	16.2.8.1	Hematology
	16.2.8.2	Chemistry
	16.2.8.3	Vital Signs
	16.2.8.4	Electrocardiogram
	16.2.8.5	Physical Examination
16.2.9		Pharmacokinetics
	16.2.9.1	Individual Plasma Concentration Data

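### SAP Section 6 stops all six adverse-event summary tables at Week 8, so no listed table delivers the time-unlimited TEAE summaries of SAP 4.8.1, and no rule says how events are grouped after the planned treatment switch

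*SAP*

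**What the plan says.** **Table list.** SAP Section 6 lists six adverse-event summaries, 14.3.1.1 to 14.3.1.6, and every title ends at Week 8. They include "Overall Summary of Treatment-Emergent Adverse Events up to Week 8 (Safety Analysis set", "Summary of Treatment-Emergent Serious Adverse Events up to Week 8 by System Organ Class and Preferred Term (Safety Analysis set" and "Summary of Treatment-Emergent Adverse Events up to Week 8 Leading to Study Discontinuation by System Organ Class and Preferred Term (Safety Analysis set". The shell package repeats the list under "Tables and Listings to Be Generated", and the first row of shell Table 14.3.1.1 reads "Number of Patients with at Least 1 TEAE up to Week 8".

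**Text on TEAEs.** SAP 4.8.1 counts as treatment-emergent any event that starts or worsens from the first dose onward and gives no end date. It states "TEAE summary will be displayed by cohort and treatment". It then lists summaries by system organ class and preferred term, by severity, by relatedness and by descending incidence. Serious TEAEs and TEAEs leading to early termination are also to be summarised, where applicable. Protocol 9.5.3 also has no end date: "A TEAE is defined as an AE that occurs (or worsens) after study drug is received". Protocol 8.5.4 collects adverse events from first dose to the end-of-study visit.

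**Treatment switch.** Under Protocol 4.1 the active group takes BBT-401-1S for 12 weeks and then placebo for 4. The placebo group takes placebo for 8 weeks and then BBT-401-1S for 8.

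**Grouping.** Protocol 9.4 groups safety patients by the treatment received. SAP 4.3.3 defines the safety set without a grouping rule. Neither document assigns an event to a period or to the product being taken at onset.

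**Endpoint.** The TEAE endpoint runs to Week 8 in Protocol 1.1, Protocol 9.5 and SAP 2.2.2. In Protocol 3 it runs to eight weeks beyond the last dose.

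**The concern.** Safety is part of the primary objective. Protocol 6.1.2 acknowledges that there is no adequate safety database in patients with active UC, and Protocol 4.3 says that Phase 1 multiple dosing lasted 7 days. Weeks 8 to 12 of the active group therefore complete the longest continuous human exposure described in the documents.

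A table list that ends at Week 8 gives no count of TEAEs, serious TEAEs or discontinuations due to events for that stretch, or for any of the placebo group's time on drug. Simply deleting the time limit from the titles would not solve it. After Week 8 the two column labels no longer describe what patients are taking, and the plan does not say what the columns then mean.

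**Working it through.** **Inputs.** 12 active and 4 placebo patients per cohort, three cohorts (Protocol 1.2, 9.2, 9.3); treatment sequences from Protocol 4.1; table cut at Week 8 from SAP Section 6. The plan states no patient-weeks figure. Its stated sample size reproduces as 3 × (12 + 4) = 48.

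**Step 1. Planned drug exposure per cohort** (patients × weeks on BBT-401-1S, full enrolment, no dropout):

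| Group | Total | To Week 8 | After Week 8 |
|---|---|---|---|
| Active | 12 × 12 = 144 | 12 × 8 = 96 | 12 × 4 = 48 |
| Placebo | 4 × 8 = 32 | 0 | 4 × 8 = 32 |
| Both | 176 | 96 | 80 |

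Share after Week 8: 80/176 = 45.5%. By group it is 48/144 = 33.3% and 32/32 = 100%. Over three cohorts it is 240 of 528.

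**Step 2. Dropout.** The documents give no dropout rate, so a fraction *d* leaving at Week 8 is assumed. The share is 80(1 − d) / [96 + 80(1 − d)].

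- d = 10%: 72/168 = 42.9%
- d = 20%: 64/160 = 40.0%
- d = 30%: 56/152 = 36.8%

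**Step 3. The 4.8.1 summaries over 16 weeks by randomised group.** The Placebo column holds 4 × 16 = 64 patient-weeks, of which 32 (50%) are on drug. The BBT-401-1S column holds 12 × 16 = 192, of which 12 × 4 = 48 (25%) are on placebo.

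**Step 4. Grouping by treatment received.** Every patient who completes Week 16 is assigned both products, so the Protocol 9.4 sentence cannot place that patient in one column. Grouping by product at onset is possible but gives unequal time. Drug has 176 patient-weeks and placebo has 32 (initial) + 48 (after active) = 80, which averages 176/16 = 11 and 80/16 = 5 weeks per patient. Of the 80 placebo patient-weeks, 48 follow 12 weeks of drug.

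**Step 5. By-visit safety tables.** Laboratory, vital-sign, ECG and examination tables are not cut at Week 8, but their shells carry only Placebo, BBT-401-1S and Overall columns. Read as randomised groups, both columns are on drug in Weeks 8 to 12 (12 × 4 + 4 × 4 = 64 patient-weeks per cohort, all on drug). In Weeks 12 to 16 each column is on the opposite product.

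**Step 6. The Protocol 3 endpoint wording.** The follow-up visit is 2 weeks (+7 days) after the last dose (Protocol 7.3), so 2 to 3 weeks are observed. Of an eight-week window from the last study-medication dose, 5 to 6 weeks are not.

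**The case against.** **The shells may be interim.** SAP Section 1 says they were created for the first cohort. They have one BBT-401-1S column although SAP 4.7.1 compares three doses with placebo, and the dose decision is made at Week 8. A Week 8 package for that decision is a plausible reading, and it stands as a caveat. It does not settle the matter: the Section 6 list carries no first-cohort label, no later set is given, and the disposition shell reports Week 16 completion.

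**A reader might infer a breach of the protocol,** since SAP Section 5 says "No changes to protocol-specified analyses are planned". The documents do not show one. Protocol 9.5 sets the TEAE endpoint at Week 8, and Protocol 9.5.2 refers its analysis to 9.5.3. That section can therefore be read as, at least partly, the analysis of the Week 8 endpoint. For serious events and events leading to withdrawal, 9.5.3 requires only listings. The firm mismatch lies inside the SAP, between 4.8.1 and Section 6.

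**Section 6 is not exhaustive.** The descending-incidence TEAE summary of 4.8.1 is not listed either, so absence from the list does not prove that full-period tables will not be produced. This makes the listings-only outcome conditional. It does not supply the missing grouping rule, which is needed whichever text governs.

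**The practical loss is limited.** Cohorts have 16 patients, no safety tests are planned, and all events are listed with onset dates. The switch weeks are fixed, so treatment at onset can be worked out by hand. The Safety Monitoring Committee receives serious events continually, and SAP 4.1 permits ad hoc analyses. All of this stands, but none of it is a planned summary.

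**Conclusion.** The point holds as an alignment gap within the SAP plus a missing rule for the switch, and it should be fixed. If Section 6 governs the final analysis, events in 80 of 176 planned drug patient-weeks per cohort (45.5%) reach listings but no adverse-event table. If SAP 4.8.1 governs and randomised group is used, half of the Placebo column's planned time is on drug.

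The figures assume 16 patients per cohort and full planned exposure. Under the assumed dropout of 10% to 30% at Week 8 the share is 42.9% to 36.8%. Confidence is moderate, because a later table set may have been intended.

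Two further inferences would go too far. Post-Week 8 events are not lost: they are collected and listed. The Week 8 tables are not wrong either: they serve the stated endpoint and the placebo-controlled comparison, which is unaffected.

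**What to change.** - Keep the six Week 8 tables and label them as the randomised comparison.
- Add to Section 6 tables of TEAEs, serious TEAEs and TEAEs leading to discontinuation over the whole treatment and follow-up period, by treatment being taken at onset. Give patient-weeks of exposure beside patient counts, and show placebo after active separately from initial placebo.
- State how events at a switch visit and during follow-up are assigned.
- Label by-visit safety columns after Week 8 by sequence (active-to-placebo, placebo-to-active).
- If the present list is meant for the first-cohort review only, say so and attach the final list.
- Separately, reconcile the Week 8 endpoint with the Protocol 3 wording, and say which last dose is meant.

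The cost is SAP and shell wording, a few extra tables and one derived variable, all from data already collected. No patients, visits or procedures are added.
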